Appendix A Case Report Forms

Institution:	MCRI On-X [®] Low Dose	Patient Initials	
Investigator:	Anticoagulation Study		
	Preoperative Data	Patient No.	
Visit Date (m/d/y)://			
Date of Birth (m/d/y):///////	Sex: Male	Female	
1. Patient has met Inclusion/Exclusion crit	teria. 🗌 Yes 📄 No (If No, atta	ach explanation)	
2. Informed Consent has been given.	$\Box_{\text{Yes}} \ \Box_{\text{No}}$ (If No, following the second sec	low notification procedure.)	
Date (m/d/y):///	(Keep signed Informed Co	nsent in patient study file.)	
3. NYHA Functional Class: \Box_{I}		IV Unknown	
4. Cardiac Rhythm: \Box Sinus \Box At \Box Paced \Box Ot	rial Fibrillation her, specify:		
5. Disease Etiology: Rheumatic	Calcific Prov	s. Valve Dysfunction	
$\Box_{\text{Congenital}}$	$\Box_{\text{Endocarditis}}$ \Box_{Deg}	generative/Myxomatous	
Other, specify:			
6. Valvular Lesions:	Aortic Mit	ral	
Stenosis			
Regurgitation			
Mixed			
Other, specify:			
7. Previous cardiac surgery: Yes			
(11 yes, sp	\Box Valve \Box A	$\square M \square T \square P$	
	ASD		
	$\Box_{\rm VSD}$		
PPM /ICD			
D _{PTCA/Stent}			
8. Pre-operative Anticoagulation Yes No			
Heparin Warfarin/Coumadin Clopidogrel Aspirin Indandione derivatives			
INR: INR Target	t Range: Date ([m/d/y):	

Institution:	MCRI On-X [®] Low Dose	Patient Initials
Investigator:	CRF 1 (p2 of 2) Preoperative Data	Patient No.

9. Preoperative risk characteristics

Ejection fraction (%0			
Left atrial systolic dimension (mm)			
Spontaneous echo contrasts	Yes	No	
Ventricular aneurysmYes	No		
Vascular pathologyYes	No		
Neurological eventsYes	No		
Estrogen replacement therapy _	Yes _	No	

10. Preoperative blood test results (AVR only)

Factor V Leiden Mutation
Prothrombin Mutation
AT-III Activity
Protein C Activity
Protein S Activity
Factor VIII Activity
Lipoproteins
Serum Thromboxane B2
Urine Thromboxane B2
Endogenous Thrombin Potential
P2Y 12

11. Patient Qualifies for Group - I) Low Risk Aortic _____, II) High Risk Aortic _____, III) Mitral _____

Investigator Signature:	Date $(m/d/y)$:	/ /
6 6		

Institution: Investigator:	MCRI On-X [®] Low Dose Anticoagulation Study CRF 2 Operative Data	Patient Initials			
Surgery Date (m/d/y)://	Surgeon:	Emergency Yes No			
Valve Information: Aortic	Size:n	nm Serial #:			
Mitral	Size:m	m Serial #:			
Concomitant Cardiovascular Procedures: CAB Valve A M ASD VSD	$\Box T \Box P \qquad \Box_{Other,}$	rysm Aortic Abdominal Ventricular Arch			
Suture Interrupted Technique:	Suture Interrupted Pledgeted Everting Mattress Noneverting Technique: Continuous Other, specify:				
Crossclamp time:Minutes					
Cardioplegia:	$Cold$ \Box $Warm$ \Box Bo	th			
	Antegrade Retrograde	Both			
Intraoperative Drugs: Heparin □ Yes □ No					
Apro	$_{\rm otinin}$ \Box $_{\rm Yes}$ \Box $_{\rm No}$				
Intraoperative Adverse Events: Ves No (If Yes, complete below.)					
Prolonged Hypotension Yes N	o Difficulty Resta	arting Rhythm 🗌 Yes 🗌 No			
Excessive Bleeding \Box Yes \Box N	o Difficulty Wear	ning from Bypass \Box Yes \Box No			
Cardiac Tamponade 🛛 Yes 🖓 N	o Study Valve Ex	planted Yes No			
Cardiac Arrest $\Box_{\text{Yes}} \Box_{\text{N}}$	o Death	\square_{Yes} \square_{No}			
Other 🗆 Yes 🗆 M	lo If Yes, explain:				
Valve Orientation: Check the most accurate valve orientation description below based upon the direction of the valve axis. Mitral: Anatomical Other, describe:					
Aortic: LC/RC commissure RC/NC commissure NC/LC commissure					
Investigator Signature:	D	ate (m/d/y)://			

Institution:	MCRI On-X [®]	Patient Initials	
Investigator:	Anticoagulation Study CRF 3	Patient No.	
Visit Date (m/d/y)//	_ □ Early PostOpe	rative/Discharge	
	\Box Interim (3	or 6 month)	
	Annual (year) (12 + 2	month interval)
	└ Off Schedule		
Group: Randomized to: Treatm	nent Control		
Patient StatusImage: Missed Follow(If follow upImage: Lost to FollowOff Schedule)Efforts toImage: Missed FollowAdverse Event	ow Up Visit. Reason, ow Up: o Contact and Results: ent (Complete Complications I	Form CRF 4)	
Type of Examination: Office/Outpaties	nt 🗌 Hospital 🗌 Telephone	□ Other	
NYHA Class: I I II		Unknown	
Cardiac Rhythm:	Regular		
Atrial Fil	prillation Other, specify:		
Anticoagulant INone	U Warfarin/Cour	nadin	
	rel Heparin		
Aspirin	□ Other		
INR Blood Collec	tion Date (m/d/y):/	_/(closest to	date of visit)
New Complications: (Since last follow up) Yes No (C	omplete complicatio	n form, CRF 4)
Echo Completed (m/d/y)	Attach CRF 6 and send echo, a	pplicable only at 1, 2	3 and 5 yr follow-up.

Investigator Signature: _____ Date (m/d/y): ____/____

Institution:	MCRI On-X [®] Low Dose	Patient Initials	
Investigator:	Anticoagulation Study CRF 4		
	Complications 1 of 2	Patient No.	
Start Date (m/d/y)://	Stop Date (m/d/y):	or \	
Duration: Week	s Days Hours	Minutes	
Etiology:			
Complication Type (check all that apply)	Complicatio	on number:	
1. Thromboembolism INeurolo	gic: 🗌 TIA 🛛 Peripheral: 🗌] Major 🔲 Cardiac: MI 🗌 Unknown	
		Minor	
	CVA] Fatal	
2 \Box Valve Thrombosis			
3. 🔲 Bleeding Event	\square Major \square Minor		
Cerebral Cardiac	Ocular GI Nose	bleed 🗌 Hematoma 🗌 Other	
4. Prosthetic Endocarditis (Organis	m:))	
Risk Factor: Dental Work	IV Drug Use \Box H	Recent Infection Other	
5. Prosthetic Valve Dysfunction			
□ Nonstructural	(Туре:)	
Structural	(Туре:)	
Paravalvular Leak	(I Minor I Major)		
6. Hemolysis (conduct blood tests)			
7. Hemolytic Anemia (conduct blood tests) Primary Secondary to:			
8. Congestive Heart Failure	Ualve Related	□ Not Valve Related	
9. \Box Reoperation	□ Repair □ Exp	blant	
10. Other Valve Related	Explain:		
11. \Box Death - Primary Cause: \Box V	alve related D Other cardiac	Other Unknown	
(continues next page	.)	

Institution	MCRI On-X®	Dationt Initials	
Institution.	Low Dose Anticoagulation Study	ratient initials	
Investigator:	CRF 4	Patient No.	
	Complications 2 of 2		
Complication number:			
Treatment: None Medication	Hospitalization	Surgery (Complete CRF5	j)
Patient Condition at Time of Event			
Cardiac Rhythm	\square_{Paced} \square_{Atria}	l Fibrillation	
Other			
NYHA Class		Unknown	
Anticoagulant Therapy 🛛 Warfarin	Clopidogrel H	eparin	
INR: Aspirin	□ _{None} □ _O	ther	
Outcome:			
Event Fully Resolved			
Permanent Impairment (Spec	vify)
)
Death Date (d/m/y):	//		
Autopsy L Y	es L _{No}		
Explant Y	es 🗌 No (If yes, com	plete CRF-5)	
Relationship to Device:			
Valve Related: Yes	🗌 No		
Lab Test Results for Hemolysis, as needed	1:		
Plasma Free Hemoglobin	Lab Upper Normal		
SLDH Lab Upper Normal	(LD1, LD2, 1	LD3, LD4	, LD5)
Reticulocyte Count Lab U	Upper Normal	_	
Serum Haptoglobin Lab L	ower Normal	-	
Investigator Signature:	Date	e (m/d/y):/	_/

Institution: Investigator:	MCRI On-X [®] Low Dose Anticoagulation Study CRF 5 Reoperative Data	Patient Initials	
	Reoperative Data		
Reoperative Procedure: Procedure Dat	te (m/d/y)://		
Study Valve Replacement (complete Explant data below)	Aortic Replacement Value Mitral Size:	ve Mfg: _mm Type:	
$\Box \text{ Study Valve Repair } \Box \text{ Aort}$	ic Specify:al		
CABG			
Pacer Implantation			
Aneurysm Repair			
	Position:		
Non Study Valve	nt Procedure:		
Repair	Replacement Valve M	fg:	
	Size:mm	Туре:	
Explant Condition: Reop C (check all that apply)	Autopsy Explant Date (1	n/d/y)://	
Pannus Overgrowth			
Thrombus			
□ Vegetation Organism:			
Other Specify:			
Valves Returned: Yes Date F	Returned (m/d/y):/	_/	
└── No If No,	Explain,		
Investigator Signature:	Date	e (m/d/y):/	/

Investigator Names:	MCRI On-X Low Dose Anticoagulation Study	Patient Initals:
Center:	CRF 6 Echocardiography Data (page 1 of 2)	Study No.:
 ECHO DATE (m/d/y): VALVE Position 	// Size Serial Number	
3. PHYSICAL ASSESSM	ENT:bpn	n heart rate
	cm ł	neight
	kg	weight
	m²	BSA
4. CARDIAC RHYTHM:	Normal sinus	
	Atrial fibrillation	
	Atrial flutter	
	Heart block: degree	
	Paced	
	Other:	
5. IMAGING:	cm LVOT diameter	· systole
6. SUBAORTIC WAVEF	DRM:m/s	Peak velocity
	mm	Hg Mean gradient
	cm	Velocity time integral

Investigator Names:	MCRI On-X LOW DOSE ANTICOAGULATION STUDY CRF_6		
Center:	Echocardiography Data (page 2 of 2) Study No.:		
Date of Echo (m/d/y)			
 RECORD ONLY DATA TRANSAORTIC WAVE 	AS APPLICABLE TO VALVE EXAMINED: EFORM (FOR AVR):m/s Peak velocity		
	mmHg Mean gradient		
	cm Velocity time integral		
7b. TRANSMITRAL WAVE	FORM (FOR MVR): m/s Peak velocity		
	mmHg Mean gradient		
	cm Velocity time integral		
	ms Pressure half-time		
8. REGURGITATION:	No Yes, please complete amount and location below: Through Paravalvular Uncertain		
	None		
	+1 Trivial/trace		
	+2 Mild		
	+3 Moderate		
	+4 Severe		
9. LEFT VENTRICULAR FU	NCTION: Normal (EF>50%)		
	Mild impairment (EF40-50%)		
	Madamta immainment (EE20, 400/)		
	Severe impairment (EF<30%)		
	Severe impairment (EF<5070)		
10. VALVE THROMBUS: No Yes. If yes, specify location and amount:			
11. OTHER ABNORMALIT	IES: Describe:		
Investigator's Signature:	Date (m/d/y):/		

Appendix D

Labeling

Appendix F

MCRI On-X LOW DOSE ANTICOAGULATION STUDY

ECHOCARDIOGRAPHIC PROCEDURES

1. General – interobserver and intraobserver variability

- 1.1 At each center, no more than two operators should perform studies.
- 1.2 At each center, one or at most two machines will be used for the study. Velocity data will be calibrated using a string phantom or equivalent device.

2. Exclusions

2.1 Poor echocardiographic window

3. Recording studies

- 3.1 Unless impossible, every study will include the following standard imaging views: parasternal long-axis, parasternal short-axis, apical 4-chamber, apical 2-chamber, apical long-axis and subcostal. Off-axis views as appropriate will also be necessary particularly to look for paraprosthetic regurgitation.
- 3.2 Doppler recordings will be made with a stand-alone continuous wave probe from apical views and for valves in the aortic position from additional right intercostals or suprasternal views. Both orthograde waveforms and, if present, regurgitant jets will be recorded.
- 3.3 Subaortic pulsed recordings will be made in the apical 5-chamber view with the sample placed just below the level at which significant flow acceleration occurs.
- **3.4** Recordings should be made with the scale set to maximize signal size and with the maximum available sweep speed.

3.5 All images and waveforms used for calculating information will be recorded on electronic media.

4. Data collected

- 4.1 Heart rate (BPM), height (cm) and weight (kg) are collected by the most convenient measure at the time of the echo exam. Body surface area (BSA) is determined from the standard nomogram or standard equation below. Geometric orifice area (GOA) is given by valve size in Table 8 of the On-X valve instructions for use. BSA $(m^2) = (Wt(kg)^{0.425} X Ht(cm)^{0.725}) X 0.007184$.
- 4.2 Diameter of the left ventricular outflow tract measured on three parasternal long-axis frames frozen in systole. Diameters will be measured from the trailing edge of the left septal echo to the leading edge of the anterior mitral leaflet echo. The maximum dimension will be taken. If there is reverberation artifact from calcium, the leading edge to leading edge convention will be used; if this artifact is excessive, the measurement will not be made. The best measurement (usually at the preoperative examination) will be assumed to remain constant throughout the study.
- 4.3 From the subaortic waveform (for prostheses in mitral or aortic positions): **peak velocity (v1), mean pressure drop (p1), velocity integral (VTI1).**
- 4.4 From the transaortic waveform (prostheses in the aortic position only): peak velocity (v₂), mean pressure drop (p₂), velocity integral (VTI₂).
- 4.5 From the mitral waveform (prostheses in the mitral position only): **Pressure half-time (PHT), mean** pressure drop, peak instantaneous early velocity (v_m), diastolic velocity integral (DVI).

- 4.6 Doppler measurements will be made over 3 cycles in sinus rhythm or over 5 to 10 cycles in atrial fibrillation (depending on clinical judgment). These will then be averaged.
- 5. Calculations

The data collected will be entered on a database and the following calculations will be performed at the central laboratory:

5.1 Effective area by the continuity equation (EOA) in the aortic position: EOA = $CSA \times VTI_1 / VTI_2$ [1]

where CSA is left ventricular outflow cross-sectional area in cm^2 calculated from the diameter assuming circular cross-section; VTI_1 is subaortic velocity integral in cm and VTI_2 is aortic velocity integral in cm.

5.2 Effective area by the continuity equation (MOA) in the mitral position: $MOA = CSA \times VTI_1 / DVI$ [2]

where DVI is diastolic velocity integral in cm

- 5.3 Effective area by the pressure half-time method (MOA1/2) in the mitral position: MOA1/2 = 220/PHT [3]
- 5.4 Peak pressure drop across the aortic value: Peak $\Delta P = 4 (v_2^2 - v_1^2)$ [4]
- 5.5 Mean pressured difference across the aortic value: Mean $\Delta P = p_1 - p_2$ [5]
- 5.6 Peak pressure drop across the mitral value: Peak $\Delta P = 4v_m^2$ [6]
- 5.7 Cardiac Output: $CO = CSA \times VTI_1 \times BPM$ [7]
- 5.8 Indexed effective orifice areas (EOAI), and cardiac index (CI): EOAI = EOA/BSA [8]; CI = CO/BSA [9]
- 5.9 Performance Index (PI): PI = EOA/GOA [10]

6. Other analyses

- 6.1 For valves in the aortic position, mean and standard deviation values will be calculated for the following parameters: peak transaortic velocity, mean transaortic velocity, mean pressure difference, peak pressure difference, effective orifice area, cardiac output and all indices.
- 6.2 For valves in the mitral position, mean and standard deviation values will be calculated for the following parameters: peak transmitral velocity, peak transmitral pressure difference, mean transmitral pressure difference, effective orifice area by continuity equation, pressure half-time and effective orifice area by pressure half-time, cardiac output and all indices.
- 6.3 The site and severity of aortic regurgitation and mitral regurgitation will be assessed.
- 6.4 The presence, site and size of any thrombus will be assessed.

CAB Coronary artery bypass

CI Cardiac index
CO Cardiac output
CRF Case report form

CSA Left ventricular outflow cross-sectional area in cm², calculated from the diameter

assuming circular cross-section

DVI Diastolic velocity integral from the mitral waveform

EOA Effective orifice area

EOAI Indexed EOA

FDA Food and Drug Administration

GOA Geometric orifice area

INR International normalized ratio

KM Kaplan-Meier LD Low dose

MOA Mitral orifice area

MOA1/2 Mitral half-time orifice area
MVR Mitral valve replacement
NYHA New York Heart Association
OPC Objective performance criteria

p₁ Mean pressure drop from the subaortic waveform
 p₂ Mean pressure drop from the transaortic waveform

PI Performance index
PHT Pressure half-time
PTYR Patient years

SAS® Statistical Analysis System

SD Standard deviation

STS Society of Thoracic Surgeons

TE Thromboembolism

v₁ Peak velocity from the subaortic waveform
 v₂ Peak velocity from the transaortic waveform

v_m Peak instantaneous early velocity from the mitral waveform

VSD Ventricular septal defect

VTI₁ Velocity integral from the subaortic waveform VTI₂ Velocity integral from the transaortic waveform

1. INTRODUCTION

This document describes the statistical methods and data presentations to be used in the summary and analysis of efficacy and safety data from Protocol 2005-01 (Clinical Trial of the On-X® Valve Using Low Dose Anticoagulation). Background information is provided for the overall study design and objectives. The reader is referred to the study protocol and case report forms (CRFs) for details of study conduct and data collection.

2. STUDY OBJECTIVE(S), TREATMENTS, AND ENDPOINT(S)

2.1 Study Objectives

The main study objective is to determine whether various patient groups with the On-X Valve can be maintained safely on lower doses of Coumadin® or on antiplatelet drugs only rather than the standard dose of Coumadin® and aspirin presently recommended by the ACC/AHA or ACCP professional societies.

2.2 Treatment Comparisons

Isolated Aortic Valve Replacement (AVR) -

Test Group I (high risk AVR) – For the first 3-months post-operation, Coumadin® at an international normalized ratio (INR) target of 2.0 to 3.0 with 81 mg/day aspirin will be used. After 3-months, the Coumadin® dose will be reduced to an INR target of 1.5 to 2.0 with 81 mg/day of aspirin continued.

Test Group II (low risk AVR) — For the first 3-months post-operation, Coumadin® at an INR target of 2.0 to 3.0 with 81 mg/day aspirin will be used. After 3-months, the Coumadin® dose will be removed and clopidogrel will be added using a loading dose of 300 mg followed by 75 mg/day with aspirin at 325 mg/day. AVR low risk patients who do not pass the hypercoagulability or drug response tests were moved to the high risk group until it was fully subscribed after which they became screen failures.

Control Groups — Postoperatively, Coumadin® will be administered for an INR target of 2.0 to 3.0 with 81 mg/day aspirin throughout the study. A separate control group will be used for each test group above.

Mitral Valve Replacement (MVR) -

Test Group III, (regardless of risk) — For the first 3-months post-operation, Coumadin® at an INR target of 2.5 to 3.5 with 81 mg/day aspirin will be used. After 3-months, Coumadin® dose will be reduced to an INR target of 2.0 to 2.5 with 81 mg/day of aspirin continued.

Control Group – Postoperatively, Coumadin® will be administered for an INR target on 2.5 to 3.5 with 81 mg/day aspirin throughout the study.

2.3 Study Endpoints

2.3.1 Safety

The primary study endpoints are the binary measures of occurrence or not of valve thrombosis, thromboembolism (TE), all major and minor bleeding events, whether or not related to drug therapy, reoperation, explant and death. The sum of all TEs (including valve thrombosis events) and major bleeding is used as the primary decision criterion for the primary endpoints.

Secondary safety study endpoints are other valve related adverse events (AEs) including the occurrence or not of endocarditis, hemolysis, hemolytic anemia, paravalvular leak and structural and non-structural dysfunction. All events shall be as defined by the AATS/STS guidelines [Akins CW, Miller DC, Turino MI, et al] for reporting valve study results.

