Test Group III, (regardless of risk) – First 3-months postoperation, Coumadin at an INR target of 2.5 to 3.5 with 81 mg/day (75 mg/day in Italy) aspirin will be used. After 3-months, Coumadin dose will be reduced to an INR target of 2.0 to 2.5 with 81 mg/day (75 mg/day in Italy) of aspirin continued.

Control Group – Postoperatively Coumadin with an INR target on 2.5 to 3.5 with 81 mg/day (75 mg/day in Italy) aspirin throughout the study.

D. Sample Size

A sample size estimate was conducted based on FDA OPC criteria^[1]. The study is expected to test the safety of low dose (LD) therapy for anticoagulant therapy in On-X valve patients with LD therapy consisting of the use of Coumadin in combination with aspirin or the use of antiplatelet therapy alone. This study is designed as a non-inferiority study requiring only that LD therapy is not inferior to standard

Coumadin/aspirin treatment. Testing the superiority of LD therapy with adverse event rates as low as expected would require exposure of a prohibitively large patient group. It was necessary for the sample size calculation to assume an acceptable event rate for the primary endpoints of thromboembolism, thrombosis and bleeding events derived by summing the FDA OPC's. The incident rate of the sum of these three events needs to be at least as low as the OPC sum, 7.3%. Table 1 gives the resulting sample size requirements based on a variety of outcomes.

The number of patients to be enrolled in the clinical trial is based first on the ability to show that linearized adverse event rates for the primary endpoints in the test groups are not inferior to the corresponding control groups and second on the ability to show that all valve related adverse event rates in the test groups do not equal or exceed 2 times the rates determined to be acceptable for mechanical valves.

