For the first criterion above, the test group will need to have less than 6%/ptyr cumulative rate of the three events for the study to reach significance with a randomized patient population of between 150 and 250 per group followed for between 5 and 6.7 years at a statistical power of 80% with type I error of 0.05 and a maximum allowable difference between groups of 1.5%. It is expected that each of 50 centers will be able to enroll an average of 30 patients into the study balanced to provide adequate population in each sub-group, providing sufficient patient-years to test the hypothesis, which under the above conditions is around 1000 as shown in Table 1. Thus the study has 200 patients per group in AVR high risk with an average of 5 years of follow-up, or alternatively 150 patients in AVR low risk averaging 6.7 years of follow-up and and up to 250 MVR averaging 4 years of follow-up, providing the approximately 1000 patient-years per group estimated to meet hypothesis.

For the second criterion above, the established rates are the objective performance criteria (OPC) given in the FDA guidance document ⁽¹⁾. The adverse event rates for which OPCs are established include the primary endpoints of thrombosis, thromboembolism and bleeding and the secondary endpoints of paravalvular leak and endocarditis as listed below:

% per valve year (R_A)
0.8
3.0
3.5
1.5
1.2
1.2

In the comparison to OPCs for each adverse event, the null hypothesis being tested is that the true adverse event rate for each test group is equal to or greater than twice the acceptable rate. Rejecting the null hypothesis would conclude that the rate for the test groups is less than two times the acceptable rate. The null and alternative hypotheses can be written as:

Null hypothesis:	$R \ge 2R_A$
Alternative hypothesis:	$R < 2R_A$

Table 1

Sample Size Estimation for On-X Trial LD Therapy vs. Control

The sample size estimation is based on one-sided proportion test, which tests that the incidence rate of thrombosis, thromboembolism and hemorrhage in the LD therapy groups are at least as low as the control groups.

				Maximum Allowable	
Type I Error	Statistical	Expected	Expected	Difference	Needed
(One-sided	Power	Proportion	Proportion	between Two Groups	Patient
Test)		In Control	In Low Dose	to Declare Non-inferiority	Years
		Group	Group		
0.05	80%	7.3%	4.5%	2.0%	309
			5.0%	2.0%	398
			6.0%	2.0%	719
			7.3%	2.0%	2112
			4.5%	1.5%	381
			5.0%	1.5%	504
			6.0%	1.5%	992
			7.3%	1.5%	3739

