The primary study endpoints are the rates of occurrence of valve thrombosis, thromboembolism, all major and minor bleeding events whether or not related to drug therapy, reoperation, explant and death. Other valve related adverse events including endocarditis, hemolysis, hemolytic anemia, paravalvular leak and structural and non-structural dysfunction are secondary endpoints. All events shall be as defined by the AATS/STS guidelines ^[2] for reporting valve study results.

Effectiveness -

Effectiveness endpoints are also secondary endpoints and shall be New York Heart Association (NYHA) functional classification and the echocardiographic hemodynamic parameters of peak and mean gradient and effective orifice area (EOA). Echocardiographic exams shall also evaluate indexed EOA, performance index, cardiac output, cardiac index and amount and location of any valvular regurgitation.

B. Follow-up Regime and Intervals

The intent of the study design is to treat mechanical valve patients with less aggressive anticoagulation. The control group drug regimes are those from the recommendations for mechanical valves of the ACCP^[3] and the AHA/ACC^[4], while test group regimes are either a clopidogrel/aspirin mix for low risk aortic patients or reduced Coumadin to just below the present recommendations but with aspirin added. Patients will be maintained on Coumadin/aspirin beginning immediately postoperatively, with heparin used from operation until INR target is reached. Randomization and transfer to test group will occur at the 3-month visit. INR control will be accomplished using home monitoring with the system provided by QAS or in Italy with systems as provided within the processes used in medical care there. The patient in consultation with his/her physician will also make drug dosage adjustments.

Patients will be followed at 3 months, 6 months and 1-year, then annually thereafter until the study is completed when the patient groups reach sufficient patient-years experience at up to 8-years of follow-up for any individual patient and at least 1-year follow-up for all patients. Visits will be scheduled within 1-month of the appropriate anniversary. Follow-up will be conducted by physician visit.

C. Investigational Procedures

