4. SAMPLE SIZE CONSIDERATIONS

The study is expected to test the safety of low dose (LD) therapy for anticoagulant therapy in On-X valve patients with LD therapy consisting of the use of Coumadin® in combination with aspirin or the use of antiplatelet therapy alone. The sample size for this study was designed as a non-inferiority study requiring only that LD therapy is not inferior to standard Coumadin®/aspirin treatment. It was necessary for the sample size calculation to assume an acceptable event rate for the primary endpoints of thromboembolism, thrombosis and bleeding events derived by summing the FDA OPC's. The incident rate of the sum of these three events needs to be at least as low as the OPC sum, 7.3%.

The test group will need to have less than 6%/ptyr cumulative rate of the three events for the study to reach significance with a patient population of 200 per group followed for 5 years at a statistical power of 80% with type I error of 0.05 and a maximum allowable difference between groups of 1.5%.

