9. SAFETY ANALYSIS

9.1 Primary Analysis

The primary study endpoints are the binary measure of occurrence or not of valve thrombosis, thromboembolism, all major and minor bleeding events whether or not related to valve, reoperation, explant and death. Additionally, the sum of all TEs (including valve thrombosis events) and major bleeding will be included with the primary endpoint analyses.

For each of these binary endpoints, a Kaplan-Meier (KM) life table will be fitted and used to compare each valve treatment group and its control group. The KM analysis will adjust for select risk factors

including age and gender. In addition, the linearized rates as well as overall percentages of occurrences will be included in summary tables. Comparisons of overall percentages between each valve treatment group and its control will be made using a chi-square test or Fisher's exact test as appropriate. Linearized rates will be analyzed for differences between treatment and control groups with relative risks and 95% confidence intervals.

Analyses of mitral valve subjects will also be stratified by location (North America versus Italy) in the summary tables.

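### The SAP labels the rate endpoints binary and names no comparison that decides non-inferiority; if a first-event analysis decides, power is about 73–76%, not the stated 80%

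*SAP*

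**What the plan says.** **Protocol.** Section III.A states: "The primary study endpoints are the rates of occurrence of valve thrombosis, thromboembolism", followed by bleeding, reoperation, explant and death. Section II.D bases the first sizing criterion on linearized rates in test and control groups. It plans about 1000 patient-years per group "at a statistical power of 80% with type I error of 0.05 and a maximum allowable difference between groups of 1.5" percent. The planned groups are 200 patients for 5 years (AVR high risk), 150 for 6.7 years (AVR low risk) and up to 250 for 4 years (MVR). Section III.H plans both Kaplan-Meier life tables and linearized rates.

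**SAP.** Section 2.3.1 states: "The primary study endpoints are the binary measures of occurrence or not of valve thrombosis, thromboembolism (TE") and the other listed events. It makes the sum of all thromboembolic events and major bleeding the primary decision criterion. Section 9.1 lists that sum with the primary endpoints and continues: "For each of these binary endpoints, a Kaplan-Meier (KM) life table will be fitted and used to compare" each treatment group with its control. Percentages are compared by chi-square or Fisher's exact test, and linearized rates by relative risks with 95% confidence intervals. Section 4 still gives the sizing for "a patient population of 200 per group followed for 5 years at a statistical power of 80" percent, with the 1.5% margin. The margin does not appear in section 9.

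**The concern.** A binary endpoint cannot count a second event in the same patient, and a Kaplan-Meier analysis of time to first event uses no follow-up after that event. A rate per patient-year can use both. The two definitions therefore give different counts from the same data, and the patient-year sizing belongs to the rate.

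Three kinds of comparison stand side by side in SAP 9.1, and none is designated. None of them, as written, tests the powered quantity, which is a difference of 1.5 percentage points per year. A test of percentages for a difference has no margin, and a relative risk is on another scale. The deciding analysis could be chosen after the data are seen, and the power in SAP 4 would not describe some of the choices. For a non-inferiority claim about safety, that is a real weakness.

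**Working it through.** **Inputs (Protocol II.D).**
- Control rate 0.073: "The incident rate of the sum of these three events needs to be at least as low as the OPC sum, 7.3" percent.
- Test rate 0.060: "the test group will need to have less than 6%/ptyr cumulative rate of the three events".
- Margin 0.015, one-sided alpha 0.05, power 80%.
- Method: "The sample size estimation is based on one-sided proportion test", with patient-years as units.
- Needed patient-years in Table 1 for this row: 992, used as about 1000.

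**Step 1: reproduce the plan's figure.** The events are adverse, so the distance to the margin is 0.015 + (0.073 − 0.060) = 0.028. With unpooled binomial variance:

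n = [0.073 × 0.927 + 0.060 × 0.940] × (1.645 + 0.842)² / 0.028² = 0.12407 × 6.183 / 0.000784 ≈ 979.

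This is within 1.3% of 992. Poisson variance gives 1049, so the binomial form is much the closer to the plan's.

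**Step 2: power at full exposure.** Power = Φ(0.028/SE − 1.645). At 1000 patient-years per group:
- Binomial: SE = √(0.12407/1000) = 0.01114, power 80.8%.
- Poisson: SE = √(0.133/1000) = 0.01153, power 78.3%.

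**Step 3: exposure if only first events count.** With a constant hazard λ, common follow-up T and no attrition, exposure = N(1 − e^(−λT))/λ. For control, 200 × 5: 200 × (1 − e^(−0.365))/0.073 = 838.

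**Step 4: power at that exposure**, from the Step 2 formula with unequal exposures:

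| Design | Full patient-years | First-event, control / test | Loss, control / test | Power, binomial | Power, Poisson |
|---|---|---|---|---|---|
| 200 × 5 | 1000 | 838 / 864 | 16% / 14% | 74.9% | 72.3% |
| 150 × 6.7 | 1005 | 795 / 828 | 21% / 18% | 73.1% | 70.5% |
| 250 × 4 | 1000 | 867 / 889 | 13% / 11% | 76.1% | 73.5% |

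For 200 × 5 the expected counts are 73 against 60 events (all events), or 61 against 52 (first events).

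**Step 5: percentages of patients.** SAP 9.1 gives no margin on this scale. One way to supply it is to carry a rate of 0.073 + 0.015 = 0.088 to the same horizon. For 200 × 5 the proportions are 30.6% (control) and 25.9% (test), and the margin is 5.0 points. SE = 0.0450, so power = Φ((0.0502 + 0.0466)/0.0450 − 1.645) = 69%. The other two designs give 66% and 71%.

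**What cannot be computed.** All of this uses the three-event sum on which the trial was sized. The SAP's criterion counts only major bleeding, and the documents give no expected rate for thromboembolism plus major bleeding.

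**The case against.** The strongest reply is that the rate analysis never left the plan. SAP 9.1 analyses linearized rates, SAP 7.2 refers to linearized rates and event counts, and SAP 14.1 lists many linearized-rate tables. The decision criterion is called a sum of events. Protocol III.C records a new unrelated event separately, and Protocol III.F keeps test patients with events in follow-up and analysis. All of that stands. A reader might infer that under this plan each patient stops contributing at the first event, so that the exposure is lost outright. Neither document says so; the loss depends on which comparison decides.

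A reader might also infer that the SAP introduced first-event analysis. It did not: Kaplan-Meier is in Protocol III.H. The SAP is dated April 2011 and the protocol revision March 2014, so the documents do not show which wording came from which.

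Setting 71–74% against the stated 80% is also tempting, but it mixes two variance formulas. Like for like, the loss is about 5–8 points on either formula.

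Finally, counting all events may not recover the power. If patients differ in underlying risk, repeat events cluster. With a gamma frailty of variance k (an assumption; the documents give none), Poisson-type power for 200 × 5 is, all events against first events: 78.3% against 72.3% at k = 0, 72.6% against 70.7% at k = 0.5, and 67.6% against 69.6% at k = 1. The power advantage of all events therefore shrinks and can reverse. This limits what the fix can promise, but it does not settle which analysis decides.

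The reply does not remove the gap. SAP 9.1 applies the binary label to the sum as well, reports rates in addition, and leaves the rate difference and its margin out.

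**Conclusion.** The point holds as a conflict of definition plus a missing designation. The protocol's endpoint is a rate with a margin per year. The SAP's endpoint is binary, with three kinds of comparison, none designated as deciding and none tied to the margin.

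The power consequence is conditional. If a first-event analysis decides, power for the sized three-event sum is about 73–76% against about 81% on the binomial formula, or about 71–74% against about 78% with Poisson variance. The 80% in SAP 4 would then not apply. These figures rest on 7.3% and 6.0% per year, constant hazards, equal follow-up, no attrition and one-sided 0.05. They should not be read as the power of the thromboembolism-plus-major-bleeding criterion. If the linearized-rate difference decides, the planned exposure of about 1000 patient-years stands, and so does the stated power on the plan's own formula, which makes no allowance for clustering of repeat events.

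**What to change.** In SAP 2.3.1 and 9.1, name one deciding analysis for each test group: the difference, test minus control, in linearized rates of all qualifying post-randomization events. Compare its upper confidence limit with 1.5 percentage points per year, use a patient-clustered (robust) variance, and state the confidence level. Say explicitly that repeat events and later patient-years count. Keep Kaplan-Meier and percentages of patients as supportive.

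The cost is SAP wording and a robust variance in the programming. Heterogeneity between patients will widen the interval, so the change restores agreement with the protocol's endpoint and margin without guaranteeing 80% power.

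If the binary definition is kept, restate the power in SAP 4 and Protocol II.D as about 73–76% on the plan's formula, with its assumptions, and define the margin on the scale that will be tested. The cost is a less favourable stated power. In either case, the SAP should give an expected rate for thromboembolism plus major bleeding, so that the power of its own criterion can be stated.
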